13.5 Data collection

The data in this trial will be recorded on paper CRFs, as per data management and quality assurance procedures described in [Section 0](#). When the data on the CRFs has been verified (by the study monitor) against source data they will be sent for data entry. All CRFs will be signed by the principal investigator.

Data entry will be conducted using the verified CRFs as source. All data entry will be controlled using proof reading.

When data from all subject's CRFs are entered into the data base a clean file meeting will be held. At that meeting it will be decided if any of the subjects should be excluded from statistical analysis.

When it has been decided which subjects should be included in the data analyses, the trial database will be locked and a copy of the it will be sent for statistical analyses.

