Statistical analyses	
All subjects who have completed the trial will be included in the statistical evaluation.
 
No statistical tests will be conducted. Confidence intervals may be constructed and will then be 2-sided and of 95% confidence.
 
Continuous data will be summarised using descriptive statistics (N, mean, median, standard deviation, minimum and maximum). Categorical data will be summarised by frequency tables (numbers and percentages).
 
Unless otherwise stated, all analyses will be done on observed cases without any substitution of missing values.

Schedule of Assessments

Visit/Contact	1	2	3	4	5
	Pre-screening	Screening	MRE examination	Blood sampling	F-U ⁽¹⁾ and early termination
Day	-21 to -1	0	14	15	Visit 2 +2 days
Visit window (days)			+/- 7 days	-	+ 2
Subject information	X	X			
In/exclusion criteria	(X) ⁽²⁾	X			
Informed consent		X			
Physical examination		X			
Pregnancy test ⁽³⁾		X			
Creatinine blood sample		X			
Subject demographics (incl. height and weight)		X			
Concomitant treatment	X	X	X	X	X
Concomitant illnesses	X	X			
Medical history	X	X			
Adverse event(s) recording			X ⁽⁴⁾	X	X
Placement of IV antecubital cannula			X ⁽⁵⁾		

Visit/Contact	1	2	3	4	5
	Pre-screening	Screening	MRE examination	Blood sampling	F-U ⁽¹⁾ and early termination
Day	-21 to -1	0	14	15	Visit 2 +2 days
Visit window (days)			+/- 7 days	-	+ 2
MRE Scan			X		
Dispensing of Lumentin® 44			X		
Administration of Gd contrast (6)			X		
Administration of Buscopan® (6)			X		
Evaluation of extension and distension of bowel filling agents			X		
Blood sampling			X ⁽⁵⁾ (pre-, 1, 2, 4, 6, 8h)	X (24h)	
Compliance			X		

- 1) Subjects will be contacted by telephone two to four working days post MRE assessment.
- 2) Only some of the criteria will be checked including, inclusion criterion 1 and exclusion criteria 2, 3, 4, 5, 6, 7, 8, 12 and 13.
- 3) Urine pregnancy test of all females who are not surgically sterile (hysterectomy or tubal ligation) or postmenopausal (i.e., experienced 12 consecutive months without menstruation).
- 4) Telephone interviews will be conducted 2 days after MRE assessment to investigate if any AEs occurred during the first days after the imaging procedure
- 5) An IV antecubital cannula will be placed for pre-blood samples and used during the first 8h including administration of gadolinium during the MRE procedure. Thereafter it will be discarded. Blood sampling on the following day (24h time point) will be drawn without a cannula.

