8.3 Subject Withdrawal and Replacement

8.3.1 *Withdrawal from Trial Therapy*

Subjects must be withdrawn if the intake of the contrast agent has to be stopped, please see section 9.2 Dosage and Administration.

8.3.2 *Withdrawal from Study*

Subjects may withdraw from the trial at any time and for any reason without prejudice to his or her future medical care.

Subjects must be withdrawn under the following circumstances:

- The subject withdraws consent
- Subjects who have not fasted (clear water allowed) for at least six hours prior to the intake of the contrast agent
- The subject is unable to drink at least 1.1 L of Lumentin® 44
- The subject is unable to complete the MRE examination, due to e.g., claustrophobia.
- Violation of eligibility criteria

Subjects withdrawn due to the above circumstances will be replaced by one of the five remaining eligible HV subjects on standby after screening.

Subjects may be required to withdraw after discussion with the Sponsor and/or Investigator for the following reasons:

- AEs
- Use of prohibited medication (see Section 10)
- At the discretion of the Investigator

In all cases, the reason(s) for withdrawal must be recorded on the Case Report Form (CRF). If a subject is prematurely withdrawn from the trial for any reason, the Investigator must make every effort to perform the evaluations described for the Early Termination Visit (see Section **Fel! Hittar inte referenskälla.**).

If a subject has withdrawn informed consent and still agrees to attend the Early Termination Visit, this will be documented on the CRF.

For subjects who are withdrawn after they receive the trial drug, the Early Termination page will be completed in the CRF.

HVs withdrawn prior or during the MRE examination (i.e., no evaluable MRE scan has been generated) will be replaced by a new HV. HVs withdrawn after the completion of MRE examination and NOT fulfilling the mandatory criteria for withdrawal listed above will not be replaced.

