13.2 Sample Size

A total of 10 fully evaluable healthy volunteers will be included in the trial. The number of subjects is considered to be enough to draw clinical conclusions and is not based on any mathematical grounds.

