13.3 Analyses Sets

All subjects who have fulfilled the trial will be included in the statistical evaluation.

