15.5 Case Report Forms (CRFs)

Data collected in this trial will be by means of paper CRFs.

The CRFs must be maintained in an up-to-date condition at all times by the investigator. The investigator, or sub-investigator(s) authorised by the investigator, will sign all sections of CRFs used. This signature information (incl. date of signature) will be kept in the audit trail and is unalterable. Only appropriately medically qualified (sub)investigators can sign data on clinical assessments/safety. Any correction(s) made by the investigator, or authorised site staff, to the CRF after original entry will be documented in the audit trail. Changes to data already approved, requires the re-signature of investigator or authorised staff. The audit trail will identify the person making the change and the date, time and reason for the change.

The trial monitor will check the CRFs for accuracy and completion and perform source data verification. For archiving purposes, each investigator will be supplied with a copy of the CRFs, for all patients enrolled at the site. Audit trail information will be included. CRFs will be available for inspection by authorised representatives from Lument AB, from Regulatory Authorities and/or IEC.

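### The only analysis set is trial completers, so subjects who took Lumentin 44 and were then withdrawn can drop out of the adverse-event summary; 13.5 adds late exclusions with no listed grounds

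*Combined protocol and SAP*

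**What the plan says.** **Analysis set.** Section 13.3: "All subjects who have fulfilled the trial will be included in the statistical evaluation". The synopsis uses a different verb: "All subjects who have completed the trial will be included in the statistical evaluation". Section 13.2 adds a third term: "A total of 10 fully evaluable healthy volunteers will be included in the trial". None of the three is defined, and no other set is described for any outcome.

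**Withdrawal and replacement.** Section 8.3.1: "Subjects must be withdrawn if the intake of the contrast agent has to be stopped". Section 9.2 names an adverse event as a cause of stopping, and 8.3.2 and 9.2 both withdraw a subject who cannot drink 1.1 L. Under 8.3.2, anyone withdrawn before or during the MRE, with no evaluable scan, is replaced. A subject withdrawn after a completed MRE without a mandatory ground is not. Subjects withdrawn after receiving the product have an Early Termination page in the CRF.

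**Safety.** Safety and tolerability is a secondary objective (6.2), with TEAEs and TEADRs as the outcome (7.2.2).

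**Exclusions.** Section 13.5: "When data from all subject's CRFs are entered into the data base a clean file meeting will be held", and then "At that meeting it will be decided if any of the subjects should be excluded from statistical analysis". The database is locked and sent for analysis after that decision. Section 15.6 goes from entry and proofreading to lock without mentioning the meeting.

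**The concern.** A safety summary should count everyone exposed. Here the subjects most informative about tolerability, those who could not go on drinking, are the ones the plan withdraws and replaces. If the tables then cover only those who finished, ten clean completers can be reported while the events that stopped intake appear in no table. The data would exist on the CRF; what is missing is a rule that brings them into the summary.

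The second matter is smaller. The trial is single-arm with ten subjects, and its results are frequency tables and possibly confidence intervals. A meeting that may exclude subjects once all data are entered, with no listed grounds, leaves a reader unable to check an exclusion against a rule set beforehand.

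**Working it through.** The sample size of 10 is stated to have no mathematical basis, so there is no planned figure to reproduce. The check is a reading of the passages, followed by two illustrations on assumed counts.

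**1. Path of a subject who takes the product and stops.**
- An adverse event during drinking stops intake and leads to withdrawal (9.2, 8.3.1). Failure to reach 1.1 L leads to withdrawal (8.3.2, 9.2), and 11.2.7 rules out the scan.
- No evaluable scan exists, so the subject is replaced (8.3.2).
- The subject has not completed or fulfilled the trial in any ordinary sense, and 13.3 names no other set.
- Sections 12.2 and 11.2.5 have adverse events recorded, but neither says which subjects the tables cover.

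**2. Is such a withdrawal likely?** The documents give no withdrawal rate. If each subject had probability p of stopping for an adverse event (assumed), the chance of at least one among the first 10 is 1 − (1 − p)^10: 40% at p = 5%, 65% at 10%, 89% at 20%. On volume, section 7.3.2 gives an average of 1026 mL drunk in earlier trials, 74 mL below this trial's 1.1 L minimum. The range requested there (0.75–1.5 L) and the populations differed, so this shows plausibility, not a rate.

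**3. Effect on the safety summary.** Assume 10 completers without the event and w subjects stopped for it and replaced, with w up to the five standby subjects in 8.3.2. Completers only: 0/10. All who took the product: w/(10 + w). Intervals are exact (Clopper–Pearson) 95%.

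| w | Completers only | All who took the product |
|---|---|---|
| 1 | 0/10 = 0% (0–30.8%) | 1/11 = 9.1% (0.2–41.3%) |
| 2 | 0/10 = 0% (0–30.8%) | 2/12 = 16.7% (2.1–48.4%) |
| 3 | 0/10 = 0% (0–30.8%) | 3/13 = 23.1% (5.0–53.8%) |
| 5 | 0/10 = 0% (0–30.8%) | 5/15 = 33.3% (11.8–61.6%) |

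With w = 0 the two summaries agree. Assuming no such event among completers makes the contrast as large as it can be for each w.

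**4. Effect of one exclusion from the image scores.** The plan sets no threshold; assume a score of 3 or more is acceptable, with k of 10 acceptable.
- Dropping one low scorer: k/9 − k/10 = k/90, from 0 (k = 0) to +10.0 points (k = 9). At k = 8, 80% (44.4–97.5%) becomes 8/9 = 88.9% (51.8–99.7%), +8.9 points.
- Dropping one acceptable scorer: (k − 1)/9 − k/10 = −(10 − k)/90. At k = 8 this gives 7/9 = 77.8%, −2.2 points.

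The interval at 8/10 is 97.5 − 44.4 = 53.1 points wide, so either shift is small beside the sampling uncertainty.

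**5. Subjects whose status is open.** A subject withdrawn after a completed MRE without a mandatory ground is not replaced. Nothing says whether that subject completed the trial, so whether the scan counts is undecided.

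**6. Adverse-event start point.** Section 11.2.5 starts recording at consent and 12.2 at intake, while section 12 does not report occurrences before the MRE assessment. An event that stops intake precedes the MRE, so on section 12's wording it might not be counted even with a proper safety set.

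**The case against.** *The safety omission is not stated.* Correct. Section 13.3 says who will be included, not that only they will be. Section 13.4 is garbled and may be meant to cover all collected data; 7.2.2 speaks of any TEAE; section 12 has all events throughout the trial recorded and followed. A reader might infer that the plan expressly removes adverse-event withdrawals from the safety tables. It does not. What stands is that no passage names a set containing them, and the one set described does not naturally hold them.

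*The meeting precedes lock and analysis.* Also correct, and it counts in the plan's favour. A reader might infer that subjects would be excluded because of poor image scores. No passage says so, and 11.3.1 does not say where the radiologist's scores are recorded; that they are on the CRF is inferred from 13.5 ("The data in this trial will be recorded on paper CRFs") and 15.5 ("Data collected in this trial will be by means of paper CRFs"). What stands is that no grounds are listed and nothing keeps the scores out of the decision.

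*Sections 13.3 and 13.5 need not conflict.* The meeting may simply apply 13.3, and 8.3.2 partly explains what evaluable means. That is the better reading: the link is missing, and the terms to be applied are undefined.

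*The figures are invented.* The counts are assumed and labelled so. Section 5.4 reports only mild to moderate events earlier, so withdrawals may be few.

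The Data Management Plan cited in 15.6 is not among the documents and might hold exclusion rules; that cannot be judged here.

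**Conclusion.** The point holds, with safety as its main part. On the natural reading of 13.3, subjects who took Lumentin 44 and were withdrawn for an adverse event or for insufficient intake are outside the TEAE/TEADR summary, which can understate adverse-event frequency. The size depends on how many there are: nothing if none, 0% against 9% for one, and 0% against 33% for five, assuming no such event among the ten completers.

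The exclusion power in 13.5 is secondary. It is a gap in specification, not evidence of selective exclusion. With no tests planned, its effect is on the tables and intervals: at most 10 points per subject dropped, on an assumed threshold. A reduced N would be visible.

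This is a cheap improvement that should be made; it does not call the design into question.

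**What to change.** 1. **Section 13.3 and synopsis, safety set.** Add: *Safety set: every subject who took any Lumentin 44, regardless of withdrawal or replacement; all adverse-event tables use this set.* Name the set for the electrolyte tables.
2. **Section 13.3 and synopsis, image set.** Define it as every subject with a completed MRE examination after Lumentin 44 intake, including those withdrawn afterwards without a mandatory ground. State that low image quality is never a reason for exclusion. List subjects with an incomplete examination, with the reason, and do not score them on scales that 11.3.1 applies to all sequences or to the whole examination.
3. **Section 13.5.** Limit exclusions from the image set to the mandatory withdrawal grounds already in 8.3.2, documented without reference to the image scores. For a ground found after scoring, tabulate the four primary scores with and without the subject, as far as consent allows.
4. **Reconcile**, without this review choosing a rule: the adverse-event start point (11.2.5, section 12, 12.2); withdrawal for adverse events, mandatory under 9.2 and 8.3.1 when intake stops but discretionary in 8.3.2; and the lock sequence in 13.5 against 15.6.

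The cost is wording, a membership record per subject and possibly one extra table. No subjects or scans are added. The downside is that the sponsor gives up late discretion over exclusions.

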14 ETHICS

14.1 Independent Ethics Committee (IEC)

The clinical trial must be approved by/receive favourable opinion from relevant Independent Ethics Committees (IECs) prior to enrolment of subjects.

Any amendments to the approved clinical trial must likewise, as required, be approved by/receive favourable opinion from relevant IECs prior to implementation.

The appropriate regulatory authority(ies) must be notified of/approve the clinical trial, as required.

14.2 Ethical Conduct of the Trial

This clinical study was designed and shall be implemented and reported in accordance with the protocol, ethical principles laid down in the Declaration of Helsinki and the International Conference on Harmonization (ICH) Harmonized Tripartite Guidelines for Good Clinical Practice (GCP).

If any changes to the protocol are required, the protocol must be amended (see [Section 16.2](#)).

14.3 Subject Information and Consent

All subjects will receive written and verbal information regarding the trial before any trial-related procedures are performed. This information will emphasise that participation in the trial is voluntary and that the subject may withdraw from the trial at any time and for any reason. All subjects will be given the opportunity to ask questions about the trial and will be given sufficient time to decide whether to participate in the trial.

The patient's signed and dated informed consent to participate in the trial will be obtained prior to any trial related procedure is being carried out. The consent form must also be signed by the person who conducted the informed consent discussion.

The consent includes information that data will be recorded, collected, processed and may be transferred to European Economic Area (EEA) or non-EEA countries. In accordance with the EU general data protection regulation 2016/679 (GDPR), the data will not identify any persons taking part in the trial.

A copy of the subject information including the signed informed consent form will be provided to the subject, for their records.

14.4 Subject Data Protection

All information containing personal data will be handled in accordance with Swedish data protection legislation and with the EU general data protection regulation 2016/679 (GDPR).

14.5 Other Ethical and Regulatory Issues

If a significant safety issue is identified, either from an individual case report or review of aggregate data, then the Sponsor will issue prompt notification to all parties: Regulatory Authorities, Investigators and IECs.

A significant safety issue is one that has a significant impact on the course of the clinical trial or program (including the potential for suspension of the trial program or amendments to protocols) or warrants immediate update of informed consent.

14.6 Ethical Consideration statement

Our newly invented per oral agent for bowel filling prior to CT or MRE of the abdomen has revealed a good potential to improve imaging of the bowel wall in comparison to currently used contrast imaging agents. In addition, being able to use the same agent for both these procedures will offer operational benefits to diagnostic clinics.

Potential benefits for future patients include first and foremost MRE images easier to interpret, thereby facilitating diagnostics of early and hitherto silent disease, and reducing the risk of misreading. Secondly, risks of adverse effects are likely to be notably low as our new agent is food-based with 44% v/v air in water, 2% egg white protein, less than 1% buffer agent, and less than 1% foam stabilizer and taste improving additives.

15 DATA MANAGEMENT AND QUALITY ASSURANCE

15.1 Quality Assurance

The Sponsor or designee will conduct a site visit to verify the qualifications of the Investigator, inspect the site facilities, and inform the Investigator of responsibilities and the procedures for ensuring adequate and correct documentation.

The Investigator is required to prepare and maintain adequate and accurate case histories designed to record all observations and other data pertinent to the trial for each trial participant. All information recorded on the CRFs for this trial must, if applicable, be consistent with the subjects' source documentation (i.e., medical records).

Trial sites, facilities, laboratories and all data (including sources) and documentation must be available for GCP audit by Lument AB or inspection by competent authorities.

Any aspect of the trial may be subject to audit by Lument AB and/or inspection by regulatory authorities or IEC. Such audits/inspections may take place at the sponsor's site(s) or at any trial site including laboratories, pharmacies etc.

The monitor will, in case of audit, announce this in advance to the investigator and be present at the particular trial site during the audit.

The site staff should assist in all aspects of audit/inspection.

15.2 Trial Monitoring

Lument AB, as sponsor of this clinical trial, is responsible to the regulatory authorities for assuring the proper conduct of the clinical trial with regard to protocol adherence and validity of the data recorded in the CRFs. The company has therefore assigned a CRO to monitor this trial. Their duties are to serve as the principal link between investigators and Lument AB and advise the investigator on the collection and maintenance of attributable, legible, contemporaneous, original and accurate data for the trial. In addition, they will explain to the investigators any aspect of the (conduct of the) trial, including interpretation of the protocol, the purpose of collecting the specified data and reporting responsibilities.

The monitor will visit the trial sites before, during and after the trial to ensure that the trial is conducted and documented in accordance with this protocol, ICH GCP guidelines, regulatory requirements, and any trial specific documents such as CRF completion guidelines.

Monitoring visits will be conducted to confirm that e.g.:

- The rights and well-being of human subjects are protected

- The investigational team is adhering to the trial protocol
- Informed consent has been obtained from all participants
- AEs have been reported as required
- Data are being accurately recorded in the CRFs and are in accordance with source data
- IP is being stored correctly and drug accountability is being performed on an on-going basis
- IP is given to correct subject
- Facilities are, and remain, acceptable throughout the trial
- The Investigator and the site are receiving sufficient information and support throughout the trial

The CRF data will be monitored on at regular intervals. The monitoring will include source data verification (SDV) according to the SDV list and verification of data consistency over time. The Investigator and other relevant trial personnel should be available during the monitoring visits.

In order to perform their role effectively, monitors and persons involved in quality assurance and inspections (see above) will need direct access to primary subject data, e.g., medical records, appointment books, etc. The review of medical records will be performed in a manner to ensure that subject confidentiality is maintained. Because this affects the subject's confidentiality, this fact is included on the Subject Information Sheet and Informed Consent Form. The Investigator assures the Sponsor of the necessary support at all times.

This trial is organised by Lument AB, and all enquiries should be made to a member of Lument AB staff (see [Section 2](#)).

15.3 Confidentiality

All trial findings and documents will be regarded as confidential. The Investigator and members of his/her research team must not disclose such information without prior written approval from the Sponsor.

The anonymity of participating subjects must be maintained. Subjects will be identified on CRFs by their subject number. On the SAE reports and all other source documents, the subject will be identified via subject number. Documents are not to be submitted to the Sponsor that identify the subject (e.g., the signed informed consent) must be maintained in confidence by the Investigator.

